5.3.6.3. Dose Modification and Toxicity Management Guidelines for Pembrolizumab

5.3.6.3.1. Dose Modification and Toxicity Management for Immune-related AEs (irAEs) Associated with Pembrolizumab

AEs associated with pembrolizumab exposure may represent an immunologic etiology. These immune-related AEs (irAEs) may occur shortly after the first dose or several months after the last dose of pembrolizumab treatment and may affect more than one body system simultaneously. Therefore, early recognition and initiation of treatment is critical to reduce complications. Based on existing clinical trial data, most irAEs were reversible and could be managed with interruptions of pembrolizumab, administration of corticosteroids and/or other supportive care. For suspected irAEs, ensure adequate evaluation to confirm etiology or exclude other causes. Additional procedures or tests such as bronchoscopy, endoscopy, skin biopsy may be included as part of the evaluation. Based on the severity of irAEs, withhold or permanently discontinue pembrolizumab and administer corticosteroids. Dose modification and toxicity management guidelines for irAEs associated with pembrolizumab are provided in [Table 5](#).

Table 5 Dose Modification and Toxicity Management Guidelines for Immune-related AEs Associated with Pembrolizumab

General instructions:
 
 1. Corticosteroid taper should be initiated upon AE improving to Grade 1 or less and continue to taper over at least 4 weeks. 2. For situations where pembrolizumab has been withheld, pembrolizumab can be resumed after AE has been reduced to Grade 1 or 0 and corticosteroid has been tapered. Pembrolizumab should be permanently discontinued if AE does not resolve within 12 weeks of last dose or corticosteroids cannot be reduced to ≤ 10 mg prednisone or equivalent per day within 12 weeks. 3. For severe and life-threatening irAEs, IV corticosteroid should be initiated first followed by oral steroid. Other immunosuppressive treatment should be initiated if irAEs cannot be controlled by corticosteroids. 				
Immune-related AEs	Toxicity grade or conditions (CTCAEv5.0)	Action taken to pembrolizumab	irAE management with corticosteroid and/or other therapies	Monitor and follow-up
Pneumonitis	Grade 2	Withhold	Administer corticosteroids (initial dose of 1-2 mg/kg prednisone or equivalent) followed by taper	Monitor participants for signs and symptoms of pneumonitis Evaluate participants with suspected pneumonitis with radiographic imaging and initiate corticosteroid treatment Add prophylactic antibiotics for opportunistic infections
	Grade 3 or 4, or recurrent Grade 2	Permanently discontinue		

Diarrhea / Colitis	Grade 2 or 3	Withhold	Administer corticosteroids (initial dose of 1-2 mg/kg prednisone or equivalent) followed by taper	Monitor participants for signs and symptoms of enterocolitis (i.e., diarrhea, abdominal pain, blood or mucus in stool with or without fever) and of bowel perforation (i.e., peritoneal signs and ileus). Participants with \geq Grade 2 diarrhea suspecting colitis should consider GI consultation and performing endoscopy to rule out colitis. Participants with diarrhea/colitis should be advised to drink liberal quantities of clear fluids. If sufficient oral fluid intake is not feasible, fluid and electrolytes should be substituted via IV infusion.
	Grade 4	Permanently discontinue		
AST / ALT elevation or Increased bilirubin	Grade 2	Withhold	Administer corticosteroids (initial dose of 0.5- 1 mg/kg prednisone or equivalent) followed by taper	Monitor with liver function tests (consider weekly or more frequently until liver enzyme value returned to baseline or is stable)
	Grade 3 or 4	Permanently discontinue	Administer corticosteroids (initial dose of 1-2 mg/kg prednisone or equivalent) followed by taper	
Type 1 diabetes mellitus (T1DM) or Hyperglycemia	Newly onset T1DM or Grade 3 or 4 hyperglycemia associated with	Withhold	Initiate insulin replacement therapy for participants with T1DM Administer anti-hyperglycemic in participants with hyperglycemia	Monitor participants for hyperglycemia or other signs and symptoms of diabetes.

	evidence of β -cell failure			
Hypophysitis	Grade 2	Withhold	Administer corticosteroids and initiate hormonal replacements as clinically indicated.	Monitor for signs and symptoms of hypophysitis (including hypopituitarism and adrenal insufficiency)
	Grade 3 or 4	Withhold or permanently discontinue ¹		
Hyperthyroidism	Grade 2	Continue	Treat with non-selective beta-blockers (e.g., propranolol) or thionamides as appropriate	Monitor for signs and symptoms of thyroid disorders.
	Grade 3 or 4	Withhold or permanently discontinue ¹		
Hypothyroidism	Grade 2-4	Continue	Initiate thyroid replacement hormones (e.g., levothyroxine or liothyronine) per standard of care	Monitor for signs and symptoms of thyroid disorders.
Nephritis and Renal dysfunction	Grade 2	Withhold	Administer corticosteroids (prednisone 1-2 mg/kg or equivalent) followed by taper.	Monitor changes of renal function
	Grade 3 or 4	Permanently discontinue		
Myocarditis	Grade 1 or 2	Withhold	Based on severity of AE administer corticosteroids	Ensure adequate evaluation to confirm etiology and/or exclude other causes
	Grade 3 or 4	Permanently discontinue		

All other immune-related AEs	Intolerable/persistent Grade 2	Withhold	Based on type and severity of AE administer corticosteroids	Ensure adequate evaluation to confirm etiology and/or exclude other causes
	Grade 3	Withhold or discontinue based on the type of event. Events that require discontinuation include and not limited to: Guillain-Barre Syndrome, encephalitis		
	Grade 4 or recurrent Grade 3	Permanently discontinue		

¹Withhold or permanently discontinue pembrolizumab is at the discretion of the investigator or treating physician.
 
NOTE: For participants with Grade 3 or 4 immune-related endocrinopathy where withhold of pembrolizumab is required, pembrolizumab may be resumed when AE resolves to ≤ Grade 2 and is controlled with hormonal replacement therapy or achieved metabolic control (in case of T1DM).
				

5.3.6.3.2. Dose Modification and Toxicity Management of Infusion-Reactions Related to Pembrolizumab

Pembrolizumab may cause severe or life-threatening infusion-reactions including severe hypersensitivity or anaphylaxis. Signs and symptoms usually develop during or shortly after drug infusion and generally resolve completely within 24 hours of completion of infusion. Dose modification and toxicity management guidelines on pembrolizumab associated infusion reaction are provided in

[Table 6.](#)

Table 6 **Pembrolizumab Infusion Reaction Dose Modification and Treatment Guidelines**

NCI CTCAE Grade	Treatment	Premedication at Subsequent Dosing

Grade 1
 
Mild reaction; infusion interruption not indicated; intervention not indicated
	
 Increase monitoring of vital signs as medically indicated until the participant is deemed medically stable in the opinion of the investigator. 	None

Grade 2
 
Requires therapy or infusion interruption but responds promptly to symptomatic treatment (e.g., antihistamines, NSAIDs, narcotics, IV fluids); prophylactic medications indicated for ≤ 24 hrs.
	
 Stop Infusion. Additional appropriate medical therapy may include but is not limited to: 
 IV fluids Antihistamines NSAIDs Acetaminophen Narcotics Increase monitoring of vital signs as medically indicated until the participant is deemed medically stable in the opinion of the investigator. If symptoms resolve within 1 hour of stopping drug infusion, the infusion may be restarted at 50% of the original infusion rate (e.g. from 100 mL/hr. to 50 mL/hr.). Otherwise dosing will be held until symptoms resolve and the participant should be premedicated for the next scheduled dose. 
Participants who develop Grade 2 toxicity despite adequate premedication should be permanently discontinued from further study drug treatment
	
Participant may be premedicated 1.5h (\pm 30 minutes) prior to infusion with:
 
 - Diphenhydramine 50 mg po (or equivalent dose of antihistamine). - Acetaminophen 500-1000 mg po (or equivalent dose of analgesic).


Grades 3 or 4
 
Grade 3:
 
Prolonged (i.e., not rapidly responsive to symptomatic medication and/or brief interruption of infusion); recurrence of symptoms following initial improvement; hospitalization indicated for other clinical sequelae (e.g., renal impairment, pulmonary infiltrates)
 
Grade 4:
 
Life-threatening; pressor or ventilator support indicated
	
 • Stop Infusion. • Additional appropriate medical therapy may include but is not limited to: • Epinephrine** • IV fluids • Antihistamines • NSAIDs • Acetaminophen • Narcotics • Oxygen • Pressors • Corticosteroids • Increase monitoring of vital signs as medically indicated until the participant is deemed medically stable in the opinion of the investigator. • Hospitalization may be indicated. 
**In cases of anaphylaxis, epinephrine should be used immediately. Participant is permanently discontinued from further study drug treatment.
	
No subsequent dosing

Appropriate resuscitation equipment should be available at the bedside and a physician readily available during the period of drug administration. For further information, please refer to the Common Terminology Criteria for Adverse Events v5.0 (CTCAE) at https://ctep.cancer.gov/protocolDevelopment/electronic_applications/docs/CTCAE_v5_Quick_Reference_5x7.pdf.
		

Other allowed dose interruptions for pembrolizumab

Pembrolizumab may be interrupted for situations other than treatment-related AEs such as medical/surgical events or logistical reasons not related to study therapy. Patients should be placed back on study therapy within 3 weeks of the scheduled interruption, unless otherwise discussed with the sponsor. The reason for interruption should be documented in the patient's study record

5.3.7. Toxicity Management of Injection-reactions Related to Galinpepimut-S

Expected AEs from study treatment injection (any component of galinpepimut-S, excluding GM-CSF) include local erythema, edema, itching, and persistent induration at the site of injection. These events are usually mild and may appear after each administration of the study treatment. These Grade 1 and Grade 2 local injection site reactions may resolve spontaneously but they can be treated with topical creams (e.g., aloe), analgesics and/or antihistamines as per investigative site guidelines and will not require treatment interruptions or discontinuation.

Local injection site reactions of grade 3 or higher may require antihistamines, non-steroidal anti-inflammatory agents, and/or steroid therapy as per investigative site guidelines. Re-challenge of a patient after a local grade 3 event will need to be discussed with the medical monitor. Premedication with diphenhydramine 50 mg (or equivalent) and/or paracetamol (325 to 1,000 mg) at least 30 minutes prior to the next treatment injection will be required for the re-challenge. If local toxicity of grade 3 or higher persists, the patient will be moved to the off- treatment follow-up period.

Systemic events of grade 3 or grade 4 toxicity that are considered possibly related to study treatment (any component of galinpepimut-S, excluding GM-CSF) should be quickly discussed with the medical monitor. Autoimmune or hypersensitivity reactions to components of the study treatment or skin test antigens are possibilities. Patients who develop events of non-skin related autoimmune disorders or anaphylactic reactions considered possibly related to the study treatment or any of its components (other than

GM-CSF) may require appropriate care with epinephrine, antihistamines, vasopressors, fluids, and/or steroid therapy as per investigative site guidelines. The medical monitor should be contacted, and these patients will be moved to the off- treatment follow-up period.

Toxicity events related to GM-CSF should be discussed expeditiously with the medical monitor and consideration will be made to either allow the patient to continue the study treatment with or without GM-CSF or to move that particular patient to the off- treatment follow-up period. Treatment of GM-CSF related events are to be treated as per investigative site guidelines.

Toxicity will be graded in accordance with CTCAE v5.0 developed by the NCI (https://ctep.cancer.gov/protocolDevelopment/electronic_applications/docs/CTCAE_v5_Quick_Reference_5x7.pdf).

).

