5.7. Rescue Medications and Supportive Care

5.7.1. Supportive Care Guidelines for Pembrolizumab

Patients should receive appropriate supportive care measures as deemed necessary by the treating investigator. Suggested supportive care measures for the management of AEs with potential immunologic etiology are outlined along with the dose modification guidelines in [Section 5.3.6.3](#), Table 5. Where appropriate, these guidelines include the use of oral or IV treatment with corticosteroids, as well as additional anti-inflammatory agents if symptoms do not improve with administration of corticosteroids. Note that several courses of steroid tapering may be necessary as symptoms may worsen when the steroid dose is decreased. For each disorder, attempts should be made to rule out other causes such as metastatic disease or bacterial or viral infection, which might require additional supportive care. The treatment guidelines are intended to be applied when the investigator determines the events to be related to pembrolizumab.

Note: If after the evaluation of the event, it is determined not to be related to pembrolizumab, the Investigator does not need to follow the treatment guidance. Refer to [Table 5](#) in [Section 5.3.6.3.2](#), for guidelines regarding dose modification and supportive care.

It may be necessary to perform conditional procedures such as bronchoscopy, endoscopy, or skin photography as part of evaluation of the event.

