- ^t. Immediately after the patient receives the GM-CSF injection, patients are to receive galinepimut-S injected SC in the same anatomical location as the GM-CSF injection. The injection site should be on the arm, leg, or torso of the patient, and should be positioned at least 5 cm away from the previous site of study treatment injection.
- ^u. Adverse event reporting begins from the time of signing the ICF to 30 days after the last injection of any study treatment (GPS/placebo or pembrolizumab). Adverse events collected before the first injection of GM-CSF will be reported as “pre-WT1 AEs”. All AEs will be graded by

CTCAE, Version 5.0. A follow-up phone call for serious adverse events will occur 90 days after the last dose of pembrolizumab or 30 days following cessation of study treatment if the patient begins new anticancer therapy, whichever is earlier. If the patient initiates new anticancer therapy, this must be reported by the investigator.

- v. Patients who complete the study, or who discontinue because of any reason other than recurrent/refractory/relapsed disease will return to the site 30 days after their last injection for final safety follow-up and completion of EOT/ET visit.
- w. Only to occur at Week 9.
- x. Only to occur at Week 36.
- y. Only to occur at Week 54.
- z. Only to occur at Weeks 72 and 84.
- aa. Only to occur at Weeks 27 and 36.
- bb. Only to occur at Weeks 45, 54, and 63.

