All AEs must be documented on the AE pages of the eCRF and in the patient's medical record. The following attributes must be assigned: (1) description; (2) dates of onset and resolution; (3) severity (per CTCAE v5.0); (4) assessment of relatedness to the study medication (unrelated, possible, probable, definite); (5) "serious" criteria if applicable (see [Section 6.4.1.3](#) on how to report SAEs); (6) action taken; and (7) outcome (recovered/resolved, not recovered/resolved, recovered/resolved with sequelae, ongoing, or death). The investigator will actively solicit this information and assess the AEs in terms of severity and relationship to study treatment. The investigator will treat the patient as medically required until the AE either resolves or becomes medically stable. Treatment for AEs may extend beyond the duration of the study. The investigator will record treatment and medications required for treatment on the appropriate eCRF(s). In the event that a patient is withdrawn from the study because of an AE or SAE, it must be recorded on the Termination eCRF as the reason for discontinuation. The Medical Dictionary for Regulatory Activities (MedDRA) will be used to code all AEs.

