6.4.1.5. Assessment of Causality

As part of the AE documentation process, investigators are required to assess whether there is a reasonable possibility that study medications caused or contributed to an AE. This is not a factor in determining what is or is not reported in the study. If there is any doubt as to whether a clinical observation is an AE, the event should be reported. The following general guidance for assessment of causality may be used:

- Unrelated: This relationship suggests that there is no association between the study drug and the reported event.
- Possible: This relationship suggests that treatment with the study drug caused or contributed to the AE, i.e., the event follows a reasonable temporal sequence from the time of drug administration or follows a known response pattern to the study drug, but could also have been produced by other factors.
- Probable: This relationship suggests that a reasonable temporal sequence of the event with drug administration exists and, based upon the known pharmacological action of the drug, known or previously reported adverse reactions to the drug or class of drugs, or judgment based on the investigator's clinical experience, the association of the event with the study drug seems likely. The event disappears or decreases on cessation or reduction of the dose of study drug.
- Definite: This relationship suggests that a definite causal relationship exists between drug administration and the AE, and other conditions (concurrent illness, progression/expression of disease state, or concurrent medication reaction) do not appear to explain the event. The event reappears or worsens if the study drug is re-administered.

Causality will be assessed for GM-CSF and study treatments separately when the AE or SAE is clearly related to the administration of GM-CSF.

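### Section 5.3.7 and Table 5 give opposite instructions for an immune event possibly related to both galinpepimut-S and pembrolizumab, and the attribution that selects the rule need not be recorded

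*Combined protocol and SAP*

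**What the plan says.** **Galinpepimut-S rule (Section 5.3.7).** The section covers "Patients who develop events of non-skin related autoimmune disorders or anaphylactic reactions considered possibly related to the study treatment or any of its components", GM-CSF excepted. After contact with the medical monitor, "these patients will be moved to the off- treatment follow-up period". Neither sentence gives a grade, and no route back to treatment is described. The paragraph opens with Grade 3 or 4 systemic events "considered possibly related to study treatment (any component of galinpepimut-S, excluding GM-CSF"), so within this section study treatment means the galinpepimut-S preparation.

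**Pembrolizumab rule (Section 5.3.6.3.1, Table 5).** Immune-related events are handled by type and grade: continue, withhold, withhold or discontinue, or permanently discontinue. After a withhold, "pembrolizumab can be resumed after AE has been reduced to Grade 1 or 0 and corticosteroid has been tapered". A table note also allows resumption after Grade 3 or 4 endocrinopathy once it is controlled. Section 5.7.1 says when this guidance applies: "The treatment guidelines are intended to be applied when the investigator determines the events to be related to pembrolizumab".

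**Recording of causality.** Section 6.4.1.2 lists, for each adverse event, one "assessment of relatedness to the study medication (unrelated, possible, probable, definite"). Section 6.4.1.5 adds a single split: "Causality will be assessed for GM-CSF and study treatments separately when the AE or SAE is clearly related to the administration of GM-CSF".

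**The concern.** Which rule governs an immune event depends on which drug is held responsible. The two drugs are given on the same day, galinpepimut-S 30 to 60 minutes after the pembrolizumab infusion ends (Section 5.2.1), so one event can meet both triggers. One rule then ends treatment while the other may continue it or allow it to restart.

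Such events are foreseeable. Section 1.1.2.2.3 reports that 1 of 11 ovarian cancer patients given galinpepimut-S with another PD-1 inhibitor developed Grade 3 panmyositis with cardiac involvement. It was counted as a dose-limiting toxicity, which that study defined as at least possibly related to the combination.

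At stake are consistent handling across up to 20 centers and the meaning of two outputs in Section 7.6.4.1: the table of adverse events leading to treatment discontinuation, and the summary of events by relationship to treatment. If the rule followed depends on an unrecorded judgement, neither can be interpreted by agent.

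**Working it through.** No statistical figure is involved. The check is a comparison of texts and a count of Table 5.

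**1. Can both rules bind the same patient?**
- Of 16 planned galinpepimut-S doses, the first 2 are given alone. The rest, 4 + 6 + 4 = 14, fall on pembrolizumab days (Section 3.1.1, Table 8).
- Section 5.3.7 needs only a possible relation to a galinpepimut-S component. Section 6.4.1.5 allows the rating *possible* when the timing is reasonable even though other factors could also have caused the event.
- Table 5 needs the investigator to judge the event related to pembrolizumab. Nothing makes the two judgements exclusive.
- The term study treatment is not used consistently. Footnote u of Table 8 writes "any study treatment (GPS/placebo or pembrolizumab"), which is wider than the meaning in Section 5.3.7 and widens the possible overlap.

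**2. How often does Table 5 allow continuing or resuming?** Each event-by-grade entry counts once:

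| Table 5 action | All rows | Rows that include Grade 3 or 4 |
|---|---|---|
| Continue | 2 | 1 |
| Withhold | 8 | 2 |
| Withhold or discontinue | 3 | 3 |
| Permanently discontinue | 6 | 6 |
| Total | 19 | 12 |

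- All grades: 2 + 8 + 3 = 13 of 19 (68%). Counting only plain continue or withhold: 2 + 8 = 10 of 19 (53%).
- Grade 3–4 only: 1 + 2 + 3 = 6 of 12 (50%). Plain continue or withhold: 1 + 2 = 3 of 12 (25%).
- Without the catch-all row for other immune-related events, which could include skin events: 11 of 16 (69%) for all grades, and 5 of 10 (50%) for Grade 3–4.

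**3. One event followed through both rules.** Take Grade 3 hypothyroidism during co-administration, regarded as autoimmune and possibly related to both drugs. Table 5 continues pembrolizumab. Section 5.3.7 takes the patient off treatment, on either reading of its grades. No section ranks the two rules.

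**4. Does the record show which rule applied?** The required attributes hold one rating against the study medication. The only split sets GM-CSF against the study treatments taken together, and only for events clearly due to GM-CSF. Section 5.3.7 excludes GM-CSF, so that split cannot show which rule was in force. Section 5.7.1 expects a pembrolizumab-specific judgement, but the listed attributes do not require it to be recorded.

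**The case against.** The strongest reply is that the rules do not meet. Section 5.3.7 is headed as galinpepimut-S reactions, Table 5 as pembrolizumab events, and Section 5.7.1 releases the investigator from Table 5 when the event is not due to pembrolizumab. This stands in part: a reader might infer a flat contradiction, and the nominal scopes do not support that. They leave open the event possibly related to both.

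Second, the autoimmune sentence may inherit Grade 3 or 4 from the start of its paragraph, and the acute care it lists fits severe reactions. This is a fair reading. On it, one cannot say that Table 5 continues or resumes in most rows. Three of the 13 rows also permit discontinuation already, and a withhold becomes permanent if the event does not resolve, or steroids cannot be reduced, within 12 weeks.

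Third, the medical monitor must be contacted. That may reduce variation, so a reader should not infer that sites will act oppositely, only that the text permits it. The contact does not alter the instruction to move the patient off treatment.

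Three further inferences are tempting but unsupported:
- *The stopping rules are undermined.* They count serious events attributable to the study agent(s) jointly (Sections 5.3.6.1 and 5.3.6.2), so separating galinpepimut-S from pembrolizumab changes no trigger.
- *The response rate shifts by 5 to 6.7 percentage points.* That is only one patient in 20 or in 15. No event frequency is given, responses before discontinuation still count in the full analysis set, and Section 6.8.3 asks for imaging every 3 months in patients who stop without progression.
- *The case report form cannot separate the drugs.* The form is not in the documents. What can be said is that the protocol's listed attributes do not require it to.

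**Conclusion.** The point holds as an unresolved overlap. For an immune event possibly related to both agents, Section 5.3.7 ends treatment, while Table 5 continues it or leaves resumption possible in 13 of 19 event/grade rows (3 of these leave discontinuation open), or in 6 of 12 if Section 5.3.7 is limited to Grade 3–4. The documents do not say which rule prevails and do not require the deciding attribution to be recorded.

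The counts assume that the Table 5 events fall under the autoimmune disorders of Section 5.3.7, a term the protocol does not define. They count table rows and say nothing about how often such events will occur. No view is taken here on which clinical rule is right.

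**What to change.** 1. Reconcile Section 5.3.7, Section 5.3.6.3.1 with Table 5, and Section 5.7.1, so that an immune event possibly related to both agents has one stated handling. The clinical team chooses it.
2. State in Section 5.3.7 which grades the autoimmune sentence covers and what study treatment means there.
3. In Sections 6.4.1.2 and 6.4.1.5, require relatedness to be recorded separately for galinpepimut-S/Montanide, pembrolizumab, GM-CSF and, in the AML arm, the hypomethylating agent.
4. In Section 7.6.4.1, tabulate related treatment-emergent events by agent.

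The cost is one wording reconciliation and a few fields per adverse event. Against a single rating, that is 3 − 1 = 2 extra in the solid tumor arms and 4 − 1 = 3 extra in AML. Sample size, visits and the efficacy analysis are unaffected.
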